3.2 Exclusion Criteria

1. Untreated brain metastases, if not planned to be treated in this course of radiation therapy
2. Pregnancy or women of childbearing potential not willing/able to use contraception during protocol treatment

3.3 Informed Consent Process

All participants must be provided a consent form describing the study with sufficient information for participants to make an informed decision regarding their participation. Participants must sign the IRB approved informed consent prior to participation in any study specific procedure. The participant must receive a copy of the signed and dated consent document. The original signed copy of the consent document must be retained in the medical record or research file.

Remote consenting may be conducted.

3.4 Randomization Procedures

N/A

3.5 Study Timeline

Primary Completion:

We estimate the primary completion date will be Feb. 25, 2022.

Study Completion:

We estimate the study completion date will be Feb. 25, 2023.

4. TREATMENT PLAN

4.1 Pre-treatment tests

- History and physical
- Laboratory testing: CBC with differential and complete metabolic panel. Pregnancy test or documentation of adequate contraception for women of childbearing potential.

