	
5. Most recent imaging shows measurable disease as defined by RECIST 1.1
 
6. Evaluation by a Stanford medical oncologist must show:
 
 The patient is expected to continue on immunotherapy for at least three more months Imaging must show response, stable disease, or modest progression If there is modest progression, the patient must be clinically stable in terms of performance status and overall disease-related symptoms 
7. Has at least one extracranial tumor safely treatable with radical-dose radiation therapy and that has not been previously treated with radiation
 
8. ECOG performance status 0-2
 
9. Has the ability to understand and the willingness to sign a written informed consent document.
 
Exclusion Criteria:
 
 Untreated brain metastases, if not planned to be treated in this course of radiation therapy Pregnancy or women of childbearing potential not willing/able to use contraception during protocol treatment
INVESTIGATIONAL PRODUCT OR PROCEDURE	Addition of radical-dose radiation therapy to standard-of-care anti-PD-1/anti-PD-L1 immunotherapy
PRIMARY OBJECTIVE(S)	
 Determine if progression-free survival at 24 weeks with this treatment combination is improved compared to historical controls who received immunotherapy without radiation therapy (see section 12.2)
SECONDARY OBJECTIVE(S)	
 Assess acute (0-6 months) and late (>6 months) grade 3-5 toxicity Assess overall survival Correlate circulating tumor DNA (ratio of post-RT to pre-RT level) with radiographic response Correlate immune markers in peripheral blood with radiographic response Assess dose-limiting toxicity
TREATMENT SUMMARY	This trial's target population is NSCLC patients who have recently started immunotherapy, and have either response, stable disease, or modest progression on follow-up imaging. Patients with substantial progression are excluded because they are unlikely to benefit from immunotherapy even with the addition of RT. The eligible patients are at high risk for progressing within the next few months if they stay on immunotherapy. In this single-arm phase II trial (with an additional prospective registry control group), patients will remain on immunotherapy, with the addition of radical-dose radiation therapy to up to four lesions.

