4.2 Drug therapy

4.2.1 Immunotherapy administration

Patients will continue on the same anti-PD-1 or anti-PD-L1 immunotherapy that they were previously receiving. Currently available anti-PD-1/anti-PD-L1 drugs include nivolumab, generally dosed every 2 weeks or every 4 weeks, pembrolizumab, generally dosed every 3 weeks, and atezolizumab, generally dosed every 3 weeks. It is acceptable to give cytotoxic chemotherapy along with immunotherapy, but no chemotherapy can be given from 7 days before first day of protocol radiation therapy to 7 days after last day of protocol radiation therapy. For chemotherapy/immunotherapy combinations, only standard of care regimens are allowed. Currently the allowed combinations are carboplatin/pemetrexed/pembrolizumab and pemetrexed/pembrolizumab [Langer].

Laboratory monitoring for patients on immunotherapy will be performed as per standard of care. For labs required at study entry (CBC w/ diff and CMP), the medical or radiation oncologist will review and initial with date on any abnormal laboratory value/report.

As systemic therapy will be given as per standard of care, it is acceptable for immunotherapy to be given by a physician outside of Stanford ie. local oncologist, however, a Stanford physician will need to evaluate the subject at protocol specified follow up time points. Additionally, study visits may be conducted via video (i.e., MyHealth video, telehealth, telemedicine) or phone.

If there is RECIST 1.1 disease progression or unacceptable toxicity, the patient will be considered to be off of protocol therapy and will not be required to be seen at protocol specified follow up time points. After progression, it will be the decision of the treating medical oncologist whether to continue immunotherapy, switch to another therapy, or discontinue active therapy.

The treating medical oncologist may also decide to stop immunotherapy for other reasons such as an excellent sustained radiographic response to treatment. In this case, the patient should continue on the protocol follow-up schedule.

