4.3 Radiation Therapy

4.3.1 Radiation therapy overview

Radical-dose radiation therapy will be given to 1-4 extracranial lesions. Radiation therapy must be given at Stanford. The lesions to be treated are at the discretion of the treating radiation oncologist. Factors in favor of selecting a lesion include large size, progression on most recent imaging, causing symptoms, and being in a threatening location (further growth is likely to cause symptoms). A conglomerate of masses or

closely spaced masses can be considered to be one lesion.

Treatment of brain metastases is not part of protocol therapy. Brain metastases, if present, will be treated as per standard of care, generally with radiation therapy.

It is acceptable to treat the 1-4 lesions concurrently or sequentially, as long as total planned course of treatment is 10 daily sessions or less. Radiation therapy should be completed in around two weeks, though it is acceptable to extend this if necessary, for instance due to department holidays or linear accelerator downtime. Ideally, radiation therapy will start on the day of an immunotherapy infusion. However, this will not always be possible for logistical reasons. If a RT session falls on the day of an infusion, the two treatments can be given in either order.

If a lesion has previously been treated with external beam radiation therapy, it is not eligible to be treated on this study. However, it is acceptable for a radiation field to about a prior field.

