4.3.7 Radiation therapy adverse events

Potential radiation therapy adverse events depend on the treated location. We expect that most treated lesions will be in the thorax. Therefore, acute toxicity could include esophagitis causing pain with swallowing, fatigue, skin reaction, or cough.

Subacute/late toxicity could include radiation pneumonitis, lung fibrosis, chest wall fracture/rib pain, hemoptysis, large airway necrosis, heart failure, pericarditis, esophageal stricture.

Symptomatic radiation pneumonitis should be treated with inhaled or oral steroids. Severe cases should be treated with high dose oral steroids for at least a one month taper.

For treatment of extra-thoracic disease sites, acute toxicity could include skin reaction, fatigue, nausea, vomiting, dysphagia, and mucositis. Subacute/late toxicity could include skin changes/alopecia, brachial plexopathy, stroke, myelitis, bowel obstruction/perforation/fistula, spinal compression fracture, other bone fracture, radiation-induced river disease, kidney failure, change in bowel/bladder habits, sexual dysfunction.

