⁶ Blood drawn before first fraction of RT or any time up to 14 days before first fraction.

⁷ Blood drawn after last fraction of RT or any time up to 14 days after last fraction.

⁸ Optional

⁹ Labs collected prior to study and prior to each cycle of immunotherapy at the discretion of the treating medical oncologist.

¹⁰ After disease progression/unacceptable toxicity, vital status will be recorded every 6-12 months by chart review and/or telephone calls.

¹¹ Adverse events will be recorded until the 96-week follow-up visit. Starting with the 108-week follow-up visit, adverse events will not be recorded, and the history & physical exam, ECOG PS, and imaging studies will all be optional.

¹² Within 60 days prior to first dose of study radiation therapy

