5. Most recent imaging shows measurable disease as defined by RECIST 1.1					
6. Evaluation by a Stanford medical oncologist must show: 
 The patient is expected to continue on immunotherapy for at least three more months Imaging must show response, stable disease, or modest progression 					
					

c. If there is modest progression, the patient must be clinically stable in terms of performance status and overall disease-related symptoms					
7. Has at least one extracranial tumor safely treatable with radical-dose radiation therapy and that has not been previously treated with radiation					
8. ECOG performance status 0-2					
9. Has the ability to understand and the willingness to sign a written informed consent document.					
Exclusion Criteria (From IRB approved protocol)					
1. Untreated brain metastases, if not planned to be treated in this course of radiation therapy					
2. Pregnancy or women of childbearing potential not willing/able to use contraception during protocol treatment					

*All subject files must include supporting documentation to confirm subject eligibility. The method of confirmation can include, but is not limited to, laboratory test results, radiology test results, subject self-report, and medical record review.

Statement of Eligibility

By signing this form of this trial I verify that this subject is **eligible** / **Ineligible** for participation in the study. This study is approved by the Stanford Cancer Institute Scientific Review Committee, the Stanford IRB, and has finalized financial and contractual agreements as required by Stanford School of Medicine's Research Management Group.

Treating Physician Signature:	Date:
-------------------------------	-------

Printed Name:

Secondary Reviewer Signature:	Date:
-------------------------------	-------

Printed Name:

Study Coordinator Signature:	Date:
------------------------------	-------

Printed Name:

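### Section 4.1 lets documented contraception replace a pregnancy test although exclusion 2 bars pregnancy itself: a minor safety gap that is cheap to close

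*Protocol*

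**What the plan says.** Section 4.1 lists the pre-treatment tests: history and physical, two routine blood panels, and "Pregnancy test or documentation of adequate contraception for women of childbearing potential". The two alternatives carry equal weight, and no window is given for either.

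Section 3.2, criterion 2, excludes "Pregnancy or women of childbearing potential not willing/able to use contraception during protocol treatment". The synopsis and Appendix A repeat it. The criterion has two limbs: being pregnant, and not being willing or able to use contraception.

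Other places where a test could have been required:

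- Section 4.2.1 refers to "For labs required at study entry (CBC w/ diff and CMP") and names no pregnancy test.
- The section 9 calendar has rows for those two panels and none for a pregnancy test.
- Appendix A asks for supporting documentation of eligibility but leaves its form open: "The method of confirmation can include, but is not limited to, laboratory test results, radiology test results, subject self-report, and medical record review".

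The treatment that the protocol adds is described in the synopsis as "Addition of radical-dose radiation therapy to standard-of-care anti-PD-1/anti-PD-L1 immunotherapy". Section 4.3.1 states: "Radical-dose radiation therapy will be given to 1-4 extracranial lesions". Section 4.3.7 expects most lesions to be thoracic but also covers other sites, in a paragraph that begins "For treatment of extra-thoracic disease sites".

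**The concern.** The check in section 4.1 does not match the criterion that it serves. Documented contraception answers the second limb of exclusion 2. It makes pregnancy less likely but does not show that a woman is not pregnant on the day. The mismatch also runs the other way: a negative test alone says nothing about contraception during treatment. Neither alternative covers both limbs.

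At stake is fetal exposure to radical-dose radiation, which is what the trial adds to ongoing care. Section 4.3.2 allows 27 Gy in 3 fractions, 40 Gy in 10, 50 Gy in 5 or 50 Gy in 10, and the fields are not confined to the chest. Such an exposure would be severe and irreversible. The argument rests on the gravity of a single event, not on how often it would happen.

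**Working it through.** The protocol gives no figure to reproduce on this point. The check is a reading of the rules side by side, followed by a small count of whom a change could still reach.

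**Logic of the screen.** Take a woman of childbearing potential with documented contraception and an early pregnancy that she does not know about.

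1. Section 4.1: the contraception document satisfies the item, so no test is needed.
2. History and physical (section 4.1): likely to reveal a known pregnancy, but no substitute for a test when the pregnancy is unrecognised.
3. Section 4.2.1 and the section 9 calendar: they concern the two blood panels. They show only that no pregnancy test is required there, not that one is ruled out.
4. Appendix A, exclusion 2: it can be answered from self-report or record review, neither of which detects an unrecognised pregnancy.
5. Result: she can be recorded as eligible and start radiation without a test.

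**Remaining reach.** Inputs: 42 patients enrolled and treated at the time of the interim decision (section 12.2.2), and total interventional enrolment of at least 43 (section 12.3). The share of women of childbearing potential is not in the protocol; 1% to 5% is assumed.

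- Minimum remaining patients: 43 − 42 = 1
- Expected women of childbearing potential among them: 1 × 0.01 = 0.01 to 1 × 0.05 = 0.05
- Sensitivity, if 10 further patients were enrolled after the 42 (an assumption, since the protocol sets no upper limit): 10 × 0.01 = 0.1 to 10 × 0.05 = 0.5

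These are counts of women to whom the rule would apply, not of pregnancies. The chance of an unrecognised pregnancy despite documented contraception is not given either, and it would make the expected number of events smaller still.

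**The case against.** The strongest reply is that this is a deliberate and proportionate choice. Section 4.1 does not relax exclusion 2, which still bars pregnancy outright. Adequate contraception is relevant, if weaker, evidence on the pregnancy limb too. Several checks remain: history and physical, a yes/no entry for exclusion 2 with supporting documentation, and signature lines for the treating physician, a secondary reviewer and the coordinator. The population has metastatic lung cancer, at most a few further patients are affected, and section 11.1 requires IRB approval of any modification before it is used.

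Most of this stands, and it limits the weight of the point. It does not close the gap, because none of those checks would detect an unrecognised pregnancy.

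A reader might also infer more than the text supports:

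- *That the check can be 60 days old at the first fraction.* The calendar footnote reading "Within 60 days prior to first dose of study radiation therapy" governs study consent only. Nothing ties the pregnancy or contraception check to consent, so the footnote is no evidence about its timing.
- *That a test must always precede simulation.* Inclusion 4 lets a PET/CT done as part of simulation serve as the restaging scan, so simulation can come before registration. Some CT or PET/CT is needed for eligibility in any case.
- *That the gap causes exposure to immunotherapy.* Inclusion 3 requires at least four weeks of it before entry.
- *That the whole enrolment is at risk.* With 42 patients already treated, a change now reaches only those still to enter.

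**Conclusion.** The point holds as a minor safety improvement. As written, section 4.1 allows an unrecognised pregnancy in a woman with documented contraception to reach protocol radiation untested, and no other stated rule prevents it. Local radiotherapy practice may add a test, but the protocol does not say so.

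The reach is a minimum of 1 further interventional patient, and that patient depends on the DSMC allowing enrolment to continue after the interim safety analysis. This takes the 42 treated patients as the count towards the 43. The figures of 0.01-0.05 women, or 0.1-0.5 with ten more patients, rest on the assumed 1-5% share and the assumed further accrual. The documents do not support a higher grading: there is no sign that any pregnant patient was treated, and no effect on the primary analysis or the error rates. What justifies the change is the severity of the event set against the very low cost of preventing it.

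**What to change.** In section 4.1, require for women of childbearing potential both a negative pregnancy test **and** documentation of adequate contraception. Place the test in a stated window before the first radiation fraction, for example up to 14 days, which is the window section 8.1.1 already uses for the pre-radiation blood draw. Where simulation follows registration, do the test before simulation. Add a matching row to the section 9 calendar, and enter the test and its window beside exclusion 2 in Appendix A.

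The cost is one inexpensive test, already named in section 4.1, for very few patients, plus the text edits and the IRB-approved modification. The primary endpoint, alpha, power and interim safety rule stay as they are. If the protocol is to be modified for another reason, this change can go in with it.

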4.2 Drug therapy

4.2.1 Immunotherapy administration

Patients will continue on the same anti-PD-1 or anti-PD-L1 immunotherapy that they were previously receiving. Currently available anti-PD-1/anti-PD-L1 drugs include nivolumab, generally dosed every 2 weeks or every 4 weeks, pembrolizumab, generally dosed every 3 weeks, and atezolizumab, generally dosed every 3 weeks. It is acceptable to give cytotoxic chemotherapy along with immunotherapy, but no chemotherapy can be given from 7 days before first day of protocol radiation therapy to 7 days after last day of protocol radiation therapy. For chemotherapy/immunotherapy combinations, only standard of care regimens are allowed. Currently the allowed combinations are carboplatin/pemetrexed/pembrolizumab and pemetrexed/pembrolizumab [Langer].

Laboratory monitoring for patients on immunotherapy will be performed as per standard of care. For labs required at study entry (CBC w/ diff and CMP), the medical or radiation oncologist will review and initial with date on any abnormal laboratory value/report.

As systemic therapy will be given as per standard of care, it is acceptable for immunotherapy to be given by a physician outside of Stanford ie. local oncologist, however, a Stanford physician will need to evaluate the subject at protocol specified follow up time points. Additionally, study visits may be conducted via video (i.e., MyHealth video, telehealth, telemedicine) or phone.

If there is RECIST 1.1 disease progression or unacceptable toxicity, the patient will be considered to be off of protocol therapy and will not be required to be seen at protocol specified follow up time points. After progression, it will be the decision of the treating medical oncologist whether to continue immunotherapy, switch to another therapy, or discontinue active therapy.

The treating medical oncologist may also decide to stop immunotherapy for other reasons such as an excellent sustained radiographic response to treatment. In this case, the patient should continue on the protocol follow-up schedule.

4.2.2 Modality Review

For patients receiving immunotherapy at an outside facility, immunotherapy quality assurance review will be performed by one of the Medical Oncologist study investigators. This will include verifying that correct medication dosing and dose schedule are being used.

4.2.3 Anticipated Adverse Events

Adverse events from immunotherapy:

The adverse events from nivolumab, pembrolizumab, and atezolizumab are outlined in the package inserts. The most common adverse reactions are fatigue, musculoskeletal pain, decreased appetite, cough, and constipation. Other serious adverse events reported included pneumonitis, immune-mediated colitis, hepatitis, endocrinopathies, nephritis, rash, and encephalitis.

Management of pneumonitis:

Pneumonitis is of particular concern in patients with lung cancer who have recently received radiation therapy. Immune mediated pneumonitis can mimic infection, radiation pneumonitis, or lymphangitic spread of disease. If the patient is believed to have moderate immune-mediated pneumonitis, immunotherapy should be held until pneumonitis resolves. Steroids should be initiated. If a patient is believed to have severe/life-threatening immune-mediated pneumonitis, steroids should be initiated, and pulmonary consultation should be sought. Immunotherapy should be permanently discontinued. If pneumonitis is thought to be due to radiation therapy rather than immunotherapy, the medication can be continued.

4.3 Radiation Therapy

4.3.1 Radiation therapy overview

Radical-dose radiation therapy will be given to 1-4 extracranial lesions. Radiation therapy must be given at Stanford. The lesions to be treated are at the discretion of the treating radiation oncologist. Factors in favor of selecting a lesion include large size, progression on most recent imaging, causing symptoms, and being in a threatening location (further growth is likely to cause symptoms). A conglomerate of masses or

closely spaced masses can be considered to be one lesion.

Treatment of brain metastases is not part of protocol therapy. Brain metastases, if present, will be treated as per standard of care, generally with radiation therapy.

It is acceptable to treat the 1-4 lesions concurrently or sequentially, as long as total planned course of treatment is 10 daily sessions or less. Radiation therapy should be completed in around two weeks, though it is acceptable to extend this if necessary, for instance due to department holidays or linear accelerator downtime. Ideally, radiation therapy will start on the day of an immunotherapy infusion. However, this will not always be possible for logistical reasons. If a RT session falls on the day of an infusion, the two treatments can be given in either order.

If a lesion has previously been treated with external beam radiation therapy, it is not eligible to be treated on this study. However, it is acceptable for a radiation field to about a prior field.

4.3.2 Radiation dose

Either stereotactic or conventional image-guided radiation therapy can be used. SABR is preferred when feasible. Four radiation therapy schedules are allowed. The treating physician will choose between ablative and non- ablative dosing based on lesion location and size. Lesions abutting critical normal structures should have non-ablative dosing. Examples of these structures include spinal cord, small bowel, brachial plexus, large vessels/airways, and esophagus.

Dose schedules:

Ablative:

50 Gy in 5 fractions, or 50 Gy in 10

Non-ablative:

27 Gy in 3 fractions, or 40 Gy in 10 fractions

